# 7.3 Sample Size and Patient Accrual

We anticipate that this study will begin enrolling subjects in the Fall 2009 and will enroll 2 subjects a month for 30 months for a total enrollment of 60. This projection is based on the 250 newly diagnosed prostate cancer patients seen in the Department of Radiation Oncology each year, of which at least 75 should be eligible for this study.

# 7.4 Stopping Rules for Excessive Adverse Events

We estimate  $\leq 7.5\%$  of the men will experience a grade 3+ adverse event. For this study, a rate of 5% grade 3+ GU and GI adverse events (pt) according to the CTCAE version 4.0 within 24 months of the start of radiation therapy is considered acceptable. A rate of 20% is considered unacceptable. The null hypothesis (H0) is that this radiation therapy is not tolerable versus the alternative hypothesis (HA) that this radiation therapy is tolerable. With 60 patients the power to reject the null hypothesis is >90%.

The stopping and continuation rules in the Table below will be applied in two stages to the first analyzable 30 cases who received at least some treatment. Analyzable patients are defined as eligible patients who received at least some treatment. If at any stage, we show that the grade 3+ GU and GI adverse event rate may be greater than or equal to 20%, we would temporarily close the study to accrual, gather the relevant source data on the cases with grade 3+ GU and GI adverse events, prepare a statistical report summarizing the adverse event findings, and present the report to the radiation oncology and GU multidisciplinary team for review. The GU team will review all source documentation on the analyzed cases with adverse events and the statistical report summarizing the findings as soon as possible. Following the review of the data, the team will discuss the findings and make a recommendation about the study. If at the first or second stage either of the stopping rules is not met, we will continue accrual and monitoring for grade 3+ GU and GI adverse events. If we continue until the last stage, then we will either conclude "tolerability" or not.

Number of Analyzable Patients *	Reject H0 pt $\ge$ 0.2 and continue	Reject HA : $pt \le 0.05$ and stop		
15	≤2	≥ 3		
30	≤ 3	$\geq 4$		

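### The 15- and 30-patient safety boundaries test a 24-month rate with no look time or follow-up set, so a low early count can be recorded as rejecting a 20% rate

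*Combined protocol and SAP*

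**What the plan says.** Section 7.4 of the combined protocol and SAP measures the monitored rate, pt, over the 24 months after the start of radiotherapy: 5% "within 24 months of the start of radiation therapy is considered acceptable", and 20% is unacceptable. The null hypothesis is that treatment is not tolerable. The rules "will be applied in two stages to the first analyzable 30 cases who received at least some treatment", and "Analyzable patients are defined as eligible patients who received at least some treatment".

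The table allows at most 2 patients with events among 15, and at most 3 among 30. It heads that column "Reject H0 pt $\ge$ 0.2 and continue". Three or more of 15, or four or more of 30, is the stopping side. The text adds: "If at any stage, we show that the grade 3+ GU and GI adverse event rate may be greater than or equal to 20" per cent, "we would temporarily close the study to accrual", after which the cases are reviewed. If a boundary is not met at either stage, accrual and monitoring go on. On the end of the process it says "If we continue until the last stage, then we will either conclude" tolerability or not. The stated power is: "With 60 patients the power to reject the null hypothesis is >90" per cent.

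No look date, minimum follow-up or handling of patients short of 24 months is given for these counts. Section 3.1 does set follow-up conditions (3 months minimum, 120 person-years in total), but for the Grade 2+ late toxicity end-point. The censoring rule in section 7.1 covers time to late adverse events.

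**The concern.** A patient treated last week is analyzable and, if event-free, counts like one followed for the whole window. The two sides of the table react differently to that. Three events among 15 remain three events whatever happens later, so the stopping side is sound on partial data. Two events among 15 may become three or more, so the passing side is not.

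This is the plan's only numerical safety boundary. Toxicity checks and serious adverse event reporting carry no rate limit. If a pass is recorded early, accrual continues with a written statement that 20% has been rejected when it has not. How often that happens at a truly unacceptable rate depends on a look time the plan leaves open.

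**Working it through.** **Inputs from the documents.** Rates 5% and 20%, boundaries 2/3 of 15 and 3/4 of 30, 24-month window (section 7.4); 2 patients a month for 30 months, 60 in all (section 7.3); visits at 1, 3, 6, 12, 18, 24 and 36 months after radiotherapy (section 6.5).

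**Assumptions.** Patient i enters and starts treatment at month i/2; no loss to follow-up. The documents give no onset pattern for grade 3+ events, so three are used: uniform over 24 months, half of events in the first 3 months, and 80% in the first 3 months.

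**1. The plan's own power figure.** With complete data and X, Y independent Bin(15, p), the chance of passing both stages is the sum over i = 0, 1, 2 of P(X = i) × P(Y ≤ 3 − i). At p = 0.05: 0.4633 × 0.9945 + 0.3658 × 0.9638 + 0.1348 × 0.8290 = 0.925. A single test of 60 patients also exceeds 90%: 92.1% with at most 5 events (assumed one-sided 2.5% level) and 97.0% with at most 6 (5% level). The plan states no level. The figure is reproduced, but only with every patient's 24-month outcome known.

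**2. Error with complete data.** At p = 0.20: 0.0352 × 0.6482 + 0.1319 × 0.3980 + 0.2309 × 0.1671 = 0.114. The rule stops in 88.6% of trials.

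**3. When complete data exist.** Month 7.5 + 24 = 31.5 for the first 15 and 15 + 24 = 39 for the first 30. Planned accrual ends at month 30.

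**4. Earlier looks.** With looks at entry of patients 15 and 30, mean follow-up is 7.5 − 4 = 3.5 months and 15 − 7.75 = 7.25 months. With uniform onset the expected counts are 15 × 0.20 × 3.5/24 = 0.44 and 30 × 0.20 × 7.25/24 = 1.81, against 3 and 6 when complete. Exact enumeration of the joint counts gives the chance of passing both stages at a true 20% rate:

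| Wait after entry of the stage's last patient | Uniform | Half early | 80% early |
|---|---|---|---|
| 0 months | 89.6% | 56.3% | 30.8% |
| 6 months | 56.3% | 31.4% | 17.6% |
| 12 months | 26.7% | 18.9% | 14.0% |
| 15 months | 19.0% | 15.3% | 12.9% |
| 24 months | 11.4% | 11.4% | 11.4% |

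Fifteen months is the longest wait that keeps the second look within planned accrual (15 + 15 = 30). Counts can only rise with follow-up, so no onset pattern brings an early look below 11.4%.

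**5. The label at complete data.** At p = 0.20, P(X ≤ 2 of 15) = 0.0352 + 0.1319 + 0.2309 = 0.398. The exact one-sided 95% upper limit is 36.3% for 2 of 15 and 23.9% for 3 of 30. Neither count excludes 20% at that level.

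**The case against.** The best defence is that the text allows a running count. It speaks of any stage, says that monitoring continues after a pass, and defines pt over 24 months, so a patient short of 24 months arguably has no outcome yet. On that reading the boundaries for the first 15 and 30 stay open, and much of the fix restates what was meant. This is a fair reading, but the plan does not say it, and it does not correct a column that records a rejection.

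The figures in the working also rest on look times and onset patterns that the documents do not supply. The 89.6% needs looks at the moment of entry together with uniform onset. What stands without those assumptions is the direction.

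Two stronger readings are tempting. A reader might infer that the trial will declare tolerability from 30 immature patients. The documents do not establish this: the 30-patient row itself says to continue, and power is quoted for 60. It remains only a possible reading, because the table has no later row. A reader might also infer that complete follow-up would turn a pass at 15 patients into a rejection of 20%. It would not, as the 39.8% shows.

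Finally, crossing a boundary brings a temporary closure and review, and section 5.9 gives expedited reporting of certain serious events. Both limit the harm; neither supplies a rate boundary.

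**Conclusion.** The point holds for the passing side of the table. As written, the rule can record that a 20% rate has been rejected on counts that cannot show it. At a true 20% rate and planned accrual, both stages are passed in 11.4% of trials with complete data, in 30.8% to 89.6% with looks at entry, and in 14.0% to 26.7% with looks 12 months later. The ranges depend on assumed onset and look times; every earlier look computed exceeds 11.4%. Separately, the rejection label is wrong at stage 1 whatever the follow-up. The consequence that the documents support is continued accrual on false reassurance. It should be fixed, and wording is enough.

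**What to change.** 1. Keep the counts. State that the suspension and review already described are triggered as soon as the 3rd patient with a grade 3+ GU or GI event among the first 15, or the 4th among the first 30, is observed within the 24-month window. State that both boundaries stay live until those patients have completed 24 months.
2. Relabel the left column *boundary not crossed, continue*, and record no rejection of H0 at stage 1. Make any statement against a 20% rate only once the patients concerned have completed 24 months, and quote the two-stage error of 11.4% with it.
3. State whether the final stage is 30 or 60 patients. If it is 60, the table needs a decision count for 60, which it does not have.

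**Cost.** No new visits, and accrual does not wait for month 31.5 or 39. Simulation of the trigger (uniform / half early / 80% early onset; for visit detection, radiotherapy is taken to last half a month):

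| | Events known at onset | Found only at scheduled visits |
|---|---|---|
| Suspended before month 30, true 20% | 82 / 85 / 87% | about 74 / 81 / 86% |
| Median enrolled at the trigger, true 20%, trials not suspended counted as 60 | 42 / 30 / 21 | about 49 / 34 / 24 |

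Suspension before month 30 occurs in about 4–7% of trials at a true 5% rate and 13–20% at 7.5%, the upper end of the plan's own estimate. With full follow-up the printed counts already imply 7.5% and 20.8% overall.

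A simpler alternative is fixed looks after a 15-month wait, which stop 81 / 85 / 87% of trials by month 30 at a true 20% rate. The trigger's gain over that is mainly earlier suspension. With late onset it still comes after much of the accrual.

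### Section 7.4 labels its interim continuation counts as rejections of H0, and gives no cut-off or alpha for the 60-patient tolerability decision to which it attaches more than 90% power

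*Combined protocol and SAP*

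**What the plan says.** All of this is in section 7.4 (Stopping Rules for Excessive Adverse Events) unless stated.

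- **Hypotheses.** A 5% rate of grade 3+ GU and GI events "within 24 months of the start of radiation therapy is considered acceptable", and 20% is unacceptable. H0 is that the treatment is not tolerable; HA is that it is.
- **Power.** "With 60 patients the power to reject the null hypothesis is >90" percent. No type I error is given.
- **Coverage of the rules.** They "will be applied in two stages to the first analyzable 30 cases who received at least some treatment".
- **Table.** There are rows at 15 patients (2 or fewer, against 3 or more) and at 30 patients (3 or fewer, against 4 or more). The columns are headed "Reject H0 pt $\ge$ 0.2 and continue" and "Reject HA : $pt \le 0.05$ and stop". There is no row beyond 30.
- **Crossing a boundary.** The text says "we would temporarily close the study to accrual", followed by review of the cases and a recommendation.
- **Not crossing.** "If at the first or second stage either of the stopping rules is not met", accrual and monitoring go on.
- **End.** "If we continue until the last stage, then we will either conclude" tolerability or not. No count is attached to that conclusion.

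The schema page and sections 2.3 and 7.3 all give a total of 60 patients.

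**The concern.** Two things do not fit together.

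First, the left column says that H0 has been rejected at counts that are quite likely when H0 is true. Read literally, 2 events in 15 patients would already count as evidence that the rate is below 20%.

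Second, the section sets out a test, with a null, an alternative, a power and a promised conclusion, but writes down no final step for it. The power belongs to 60 patients; the counts stop at 30.

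Section 7.4 holds the plan's only rule for calling the regimen tolerable. Without a final cut-off, two analysts could differ on the same data. With 3 events in the first 30 and 7 in all 60, one who takes the heading at 30 as the test declares tolerability. One who applies an exact one-sided 5% test at 60 does not, because the upper limit for 7/60 is 20.8%.

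**Working it through.** **Inputs (section 7.4).** H0 rate 0.20; HA rate 0.05; cut-offs 2 of 15 and 3 of 30, the second taken as cumulative; 60 patients. Every patient counted is taken to have known 24-month status. Write B(c; n, p) for the exact binomial P(X ≤ c).

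**1. The plan's own figure.** No cut-off is given for 60, so take the largest c with B(c; 60, 0.20) ≤ 0.05 in a single look (the 5% level is an assumption).

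- B(6; 60, 0.20) = 0.0308 and B(7; 60, 0.20) = 0.0670, so c = 6.
- Power at 5%: B(6; 60, 0.05) = 0.9703.
- With alpha at most 2.5%, c = 5: alpha 0.0121, power 0.9213.

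Both exceed 90%, so the stated figure can be reproduced.

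**2. The counts headed as rejections of H0, at a true rate of 20%.**

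- Row 1: P(0) + P(1) + P(2) of 15 = 0.0352 + 0.1319 + 0.2309 = **0.398**.
- Row 2 taken alone: B(3; 30, 0.20) = **0.123**.
- Both rows, summing over the first 15 patients P(x) × B(3 − x; 15, 0.20): 0.0352 × 0.6482 + 0.1319 × 0.3980 + 0.2309 × 0.1671 = 0.0228 + 0.0525 + 0.0386 = **0.114**.

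The same sum at a true rate of 5%: 0.4633 × 0.9945 + 0.3658 × 0.9638 + 0.1348 × 0.8290 = **0.925**.

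**3. Do the boundary results exclude 20%?** Exact (Clopper-Pearson) one-sided 95% upper limits are 36.3% for 2/15 and 23.9% for 3/30. Neither does. Lower counts in the same cells can: the limit is 18.1% for 0/15 and 19.5% for 2/30.

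**4. A final look at 60 with the two interim looks kept.** There are two limiting cases.

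- *Stops final:* a trial that crosses at 15 or 30 can never conclude tolerability.
- *Accrual may resume:* at the limit every closed trial resumes, which is the single-look result.

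With stops final, the probability is the sum over s = 0 to 3 of P(s events in 30, first look passed) × B(c − s; 30, p).

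For c = 6 at p = 0.20: 0.0012 × 0.6070 + 0.0093 × 0.4275 + 0.0337 × 0.2552 + 0.0697 × 0.1227 = 0.0219.

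For c = 6 at p = 0.05: 0.2146 × 0.9994 + 0.3389 × 0.9967 + 0.2586 × 0.9844 + 0.1128 × 0.9392 = 0.913.

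| Final cut-off | Alpha, stops final | Alpha, may resume | Power at 5%, stops final | Power at 5%, may resume |
|---|---|---|---|---|
| ≤5/60 | 1.0% | 1.2% | 88.2% | 92.1% |
| ≤6/60 | 2.2% | 3.1% | 91.3% | 97.0% |
| ≤7/60 | 3.9% | 6.7% | 92.2% | 99.0% |

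With stops final, no cut-off at 60 can lift power above the 92.5% chance of passing both interim looks.

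**5. Fewer than 60 with known status.** The largest c with B(c; n, 0.20) ≤ 0.05 is 6 for n = 57 to 60 (alpha 4.5% at 57) and 5 for n = 50 to 56 (alpha 4.8% at 50). Suppose 60 are treated and the only ones left out are event-free patients lost to follow-up. The number of events is then still close to Binomial(60, 0.05), but it is judged against 5. Power is therefore about that of the first table row, 88.2% to 92.1%.

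**6. Timing.** At 2 patients a month, the 60th enters at month 30 and reaches 24 months at about month 30 + 24 = 54, ignoring the gap between enrolment and first fraction.

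**The case against.** The best defence is that this is a safety-monitoring section with loose headings. Both left-hand cells end with an instruction to continue, a crossing leads to review, and the power figure holds up. Much of that stands. At 15 patients the fault is one of labelling only, since passing a lenient early look is ordinary. A 5% alpha is this review's assumption, so the upper limits in step 3 illustrate the point and do not show a breach of any stated level.

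Three stronger readings are tempting, and the documents do not support them.

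- *The power is miscalculated.* It is not shown to be. It reproduces for single-look cut-offs of 5 or 6 of 60, and the 30-patient rule also has 92.5%.
- *The trial has an 11.4% type I error.* That is the chance of passing both interim looks at a true 20% rate, or at most 12.3% if accrual resumes after a first-stage crossing. It would be the error rate only if passing at 30 were the final conclusion.
- *The last stage might be 30.* The text has accrual go on when the second-stage rule is not met, and the power sentence, the schema page and sections 2.3 and 7.3 all say 60.

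Section 7.1 does not fill the gap. Its 60-patient power figures concern grade 3 or higher rectal toxicity against limits of 7.1% and 9.6%.

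The defence does not meet one point: a section that states hypotheses and power and promises a conclusion needs a final count and an error rate, and neither is written.

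**Conclusion.** The point holds as a fault in the decision rule and its specification. It is not an arithmetic error in the power figure. The counts at 15 and 30 are continuation bounds mislabelled as rejections of H0: a regimen with a 20% rate passes the first 39.8% of the time and both 11.4%. The last stage is 60 patients, and it has no cut-off or alpha. Whether power exceeds 90% depends on what is missing: 88.2% to 92.1% for 5 of 60, and 91.3% to 97.0% for 6 of 60. Within each range the figure turns on whether an interim crossing ends the trial.

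These results assume cumulative counts at 30, independent patients, and complete 24-month status. The follow-up to be counted at the interim looks, and the section's separate estimate of at most 7.5%, are different questions and are not part of this point. It should be fixed, but it leaves the primary-endpoint power in section 7.1 untouched.

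**What to change.** 1. Keep the counts at 15 and 30. Retitle the columns *Continue* and *Stop/close for review*, and remove the wording about rejecting H0 and HA.
2. Name 60 patients as the last stage and add, for example: *Conclude tolerability (reject H0: rate of 20% or more) if at most 6 of 60 analyzable patients have a grade 3+ GU/GI event within 24 months of starting radiotherapy; otherwise H0 is not rejected.* State alpha of 2.2% to 3.1% and power at a 5% rate of 91.3% to 97.0%. A cut-off of 6 keeps alpha below 5% whichever way item 4 is settled; a cut-off of 7 does not.
3. If fewer than 60 have known 24-month status, use the largest c with exact P(X ≤ c | 20%) at or below 5% and report the achieved alpha. Do not promise more than 90% power here: it is about 88% to 92% where the cut-off falls to 5 and only event-free patients are lost.
4. Reconcile stopping (table) with temporary closure pending review (text), then quote the single alpha and power that follow.

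**Cost.** Wording only: no extra patients, and no extra visits because follow-up to 36 months is already planned. The drawback is that the tolerability conclusion waits until the last patient reaches 24 months, about month 54 at the planned accrual rate.

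### Section 7.4 checks its adverse-event boundary only at 15 and 30 patients, so accrual can continue after the count has already settled that accrual must pause for review

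*Combined protocol and SAP*

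**What the plan says.** Section 7.4 sets as its tolerable level "a rate of 5% grade 3+ GU and GI adverse events (pt) according to the CTCAE version 4.0". Events count if they arise in the first 24 months after radiotherapy begins. At the other end, "A rate of 20% is considered unacceptable". The section expects that at most 7.5% "of the men will experience a grade 3+ adverse event".

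The boundary is tied to two looks: "The stopping and continuation rules in the Table below will be applied in two stages to the first analyzable 30 cases". The table continues at 2 or fewer affected men of 15 and stops at 3 or more. It continues at 3 or fewer of 30 and stops at 4 or more. The action is also tied to a look: "If at any stage, we show that the grade 3+ GU and GI adverse event rate may be greater than or equal to 20" percent, accrual is suspended, source data on the affected men are gathered, and the multidisciplinary team makes a recommendation. If a look does not meet the stopping rule, "we will continue accrual and monitoring for grade 3+ GU and GI adverse events".

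A man is analyzable once he is eligible and has had any study treatment; no minimum follow-up is required. The section does not say when each look takes place relative to the 24-month event window.

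**The concern.** The number of affected men can only rise. Once three of the first 15 have had a qualifying event, the first row of the table must read stop. Once four of the first 30 have, the second row must. Men treated after that point cannot change the result, yet the section provides no closure until a stage is reached. In the extreme case, events in the first three men could be followed by twelve more treated men before the first row applies.

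What is at stake is exposure of further men after the plan's own criterion for pausing has been met. This matters most where the true rate is near the 20% that the plan calls unacceptable. Monitoring elsewhere does not close the gap. The weekly checks (section 6.4), the toxicity visits (sections 6.5 and 6.6) and serious adverse event reporting (section 5.9) are not linked to this boundary.

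**Working it through.** **Inputs.** From section 7.4: looks at 15 and 30 analyzable men, stop at 3 or more and 4 or more, rates of 5%, 7.5% and 20%, a 24-month window. From section 7.3: 2 men per month for 30 months, 60 in all. The 30% rate and the event-time patterns in step 4 are assumptions.

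**1. The plan's own figure.** Section 7.4 says "With 60 patients the power to reject the null hypothesis is >90" percent. It gives neither alpha nor a final cut-off. With exact binomial probabilities and rejection at 6 or fewer events of 60, alpha at 20% is 0.031 and power at 5% is 0.970. Including both looks, power is 0.913 and alpha 0.022. The stated power is reproducible.

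**2. Stop probability with every event counted.** Let b(15,k) be the binomial probability of k affected men in 15.

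- Stop at look 1: S1 = 1 − [b(15,0) + b(15,1) + b(15,2)]. At 20%: 1 − (0.0352 + 0.1319 + 0.2309) = 0.6020.
- Pass both looks: Σ over k = 0, 1, 2 of b(15,k) × P(at most 3 − k in the next 15). At 20%: 0.0352 × 0.6482 + 0.1319 × 0.3980 + 0.2309 × 0.1671 = 0.1139.
- Stop at either look: 1 − 0.1139 = 0.8861.

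A patient-by-patient recursion that stops at the third event among men 1–15, or the fourth among men 1–30, gives the same stop probability at every rate tried.

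**3. Men treated through 30, if each event is known before the next man is treated.** Staged mean = 15 × S1 + 30 × (1 − S1). At 20%: 15 × 0.6020 + 30 × 0.3980 = 20.97. Men spared = S1 × (mean spared per look-1 stop) + S2 × (mean spared per look-2 stop), where S2 is the probability of stopping at look 2. At 20%: 0.6020 × 4.99 + 0.2841 × 6.43 = 4.83, so the event-driven mean is 20.97 − 4.83 = 16.14.

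| True rate | P(stop), both rules | Staged mean | Event-driven mean | Spared per stop |
|---|---|---|---|---|
| 5% | 0.0750 | 29.5 | 29.2 | 3.8 |
| 7.5% | 0.2079 | 28.5 | 27.7 | 4.1 |
| 20% | 0.8861 | 21.0 | 16.1 | 5.5 |
| 30% | 0.9915 | 16.9 | 10.4 | 6.6 |

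**4. Delayed events.** Assume 2 men per month, a true rate of 20%, and event times uniform over 24 or over 6 months from the start of treatment. The 15th man starts at month 15/2 = 7.5. A first look that waits for his 24 months falls at 7.5 + 24 = 31.5, after the planned 30 months of accrual. Simulated mean men treated, of 60, when the events each look would count are acted on as soon as they decide it:

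| Look timing | Event times | Staged | Acting early | Saved |
|---|---|---|---|---|
| When the 15th and 30th men are treated | 24 months | 56.8 | 56.3 | 0.4 (before rounding) |
| When the 15th and 30th men are treated | 6 months | 34.7 | 30.5 | 4.2 |
| After 24 months of follow-up | 24 months | 60.0 | 42.4 | 17.6 |
| After 24 months of follow-up | 6 months | 60.0 | 24.7 | 35.3 |

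**5. Chance of crossing the boundary if looks are snapshots.** Here an event-driven rule also counts events that arise after a look. With event times uniform over 24 months:

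| True rate | Snapshot looks | Event-driven, any time | Event-driven, within 30-month accrual |
|---|---|---|---|
| 5% | 0.1% | 7.5% | 5.8% |
| 7.5% | 0.5% | 20.8% | 16.3% |
| 20% | 10.5% | 88.5% | 82.0% |

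With event times over 6 months, the 7.5% row becomes 10.3% for snapshot looks against 20.8%.

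**The case against.** The strongest objection is that the event-driven wording is a different rule, not the same rule acted on sooner. A reader might infer from step 2 that every error rate is preserved whatever the look timing. The documents do not support that. With a 24-month window and no follow-up required before a look, section 7.4 can be read as two snapshots, and step 5 then shows large changes in the chance of a pause. This part of the objection stands. Equality holds only if the staged looks would have counted the same events.

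The second objection is to the size. A reader might take about five men spared per stop as the expected benefit. That needs events to be known at once, whereas section 3.1 makes late toxicity at 2 years the primary endpoint and section 7.1 defines late as more than 90 days after radiotherapy. This also stands: under snapshot looks with slow onset, the gain from acting early on the same events is close to nil. But late onset does not always shrink the gain. If looks wait for full follow-up, the gain is largest.

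Third, looks at fixed stages are a conventional choice, three events in the first three men have probability only 0.2 × 0.2 × 0.2 = 0.008 at a 20% rate, and the team would see early severe events at scheduled visits. All true, but none of this monitoring is tied to the boundary, and a written stopping rule should not rely on informal action.

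**Conclusion.** The point holds, as a change that should be made. Section 7.4 lets accrual continue after the deciding event and gives no trigger between stages. Men treated in that interval add nothing to the stop-or-continue decision. It would go too far to say that the trial's termination has become certain: the settled outcome is a suspension of accrual, a review and a recommendation.

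The size is not a single number. It is negligible at 5% (29.5 to 29.2 men, even with immediate knowledge of events). At 20% it is about 4.8 men on average through 30 if events are known at once. With delayed events at 20% it is about 0.4 to 4.2 men per trial for snapshot looks and about 18 to 35 for looks that wait 24 months. The delayed-event figures rest on 2 men per month and the assumed event-time patterns. The plan does not state the look timing that decides between them.

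**What to change.** Add one sentence to section 7.4: accrual closes for the review already described as soon as the third man of the first 15, or the fourth man of the first 30, has a grade 3+ GU or GI event within 24 months of starting radiotherapy, whether or not a stage has been reached. Keep the continue side at 15 and 30, and state when those two looks take place relative to follow-up.

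The stop probabilities then equal the table's binomial values with complete 24-month ascertainment: 7.5% at a true 5%, 20.8% at 7.5%, and 88.6% at 20%. The section should report these.

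The cost is a running count of affected men and, after a stop, a slightly smaller sample for estimating the rate. If the sponsor had intended snapshot looks, there is also a higher chance of a temporary pause at tolerable rates, up to about 21% at a true 7.5%. The sponsor should accept that openly and not describe the change as neutral.

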# **3.3** Exclusion Criteria

3.3.1 Prior or concurrent invasive malignancy (except non-melanomatous skin cancer) or lymphomatous/hematogenous malignancy unless continually disease free for a

minimum of 5 years. (For example, carcinoma in situ of the bladder or oral cavity is permissible)

- 3.3.2 Evidence of distant metastases (based on disease stage and clinical presentation)
- 3.3.3 Evidence of regional lymph node involvement (based on disease stage and clinical presentation)
- 3.3.4 Significant urinary obstruction (i.e. AUA Symptom score > 18)
- 3.3.5 Estimated prostate gland > 100 grams (within 8 weeks prior to study enrollment)
- 3.3.6 Previous radical surgery (prostatectomy) or cryosurgery for prostate cancer
- 3.3.7 Previous pelvic irradiation, prostate brachytherapy, or bilateral orchiectomy
- 3.3.8 Previous hormonal therapy, such as LHRH agonists (e.g. goserelin, leuprolide), anti-androgens (e.g., flutamide, bicalutamide), estrogens (e.g., DES), or surgical castration (bilateral orchiectomy) or planned concurrent androgen deprivation therapy
- 3.3.9 Previous or concurrent cytotoxic chemotherapy for prostate cancer
- 3.3.10 Prosthetic implants in the pelvic region that contain metal or conductive materials (e.g., an artificial hip).
- 3.3.11 Severe, active comorbidity, defined as follows:
  - Unstable angina and/or congestive heart failure requiring hospitalization within the last 6 months
  - Transmural myocardial infarction within the last 6 months
  - Acute bacterial or fungal infection requiring intravenous antibiotics at the time of registration
  - Crohn's Disease or ulcerative colitis
  - Chronic obstructive pulmonary disease exacerbation or other respiratory illness requiring hospitalization or precluding study therapy at the time of registration
  - Hepatic insufficiency resulting in clinical jaundice and/or coagulation defects; note, however, that laboratory tests for liver function and coagulation parameters are not required for entry into this protocol. (Patients on Coumadin or other blood thinning agents are eligible for this study.)
  - Acquired immune deficiency syndrome (AIDS) based upon current CDC definition; note, however, that HIV testing is not required for entry into this protocol. The need to exclude patients with AIDS from this protocol is necessary because the treatments involved in this protocol may be significantly immunosuppressive. Protocol-specific requirements may also exclude immunocompromised patients.

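### The stopping rule in Section 7.4 counts only eligible treated men, so a grade 3+ GU or GI event in an irradiated man later ruled ineligible does not count toward the boundary

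*Combined protocol and SAP*

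**What the plan says.** Section 7.4 takes as acceptable "a rate of 5% grade 3+ GU and GI adverse events (pt) according to the CTCAE version 4.0 within 24 months", counted from when radiation begins, and then states: "A rate of 20% is considered unacceptable". The rule "will be applied in two stages to the first analyzable 30 cases who received at least some treatment". The table column headed "Number of Analyzable Patients" has two rows. At 15 patients, accrual continues with 2 or fewer events and stops with 3 or more. At 30, it continues with 3 or fewer and stops with 4 or more.

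The analysis set is defined in the text and again in the table footnote: "Analyzable patients are defined as eligible patients who received at least some treatment". If a boundary is met, accrual closes temporarily, a statistical report is prepared, and the GU team reviews source documents on the analyzed cases with adverse events. No section says how an event in a treated but ineligible man enters the rule, and no all-treated safety set is defined.

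Section 3.3 lists the exclusions. They include "Significant urinary obstruction (i.e. AUA Symptom score > 18" (3.3.4), "Estimated prostate gland > 100 grams" (3.3.5), earlier pelvic irradiation or brachytherapy (3.3.7), and Crohn's disease or ulcerative colitis (3.3.11).

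**The concern.** The rule asks whether this radiation therapy is tolerable, and every man who was irradiated carries information on that. Under the definition as written, a treated man later ruled ineligible leaves both numerator and denominator, and the next eligible man takes his place.

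Two features make this more than a matter of form. First, the boundaries are so low that a single event can decide the outcome. Second, several exclusions concern the organs being monitored: heavy urinary symptoms, a very large gland, inflammatory bowel disease and prior pelvic radiation plausibly mark higher GU or GI risk. If they do, the men left out are more likely than others to have the event that the rule is watching for. Section 7.4 also does not say when, or with what knowledge of outcome, a man may be ruled ineligible.

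**Working it through.** **The plan's own figure.** Section 7.4 states: "With 60 patients the power to reject the null hypothesis is >90" per cent. It gives no alpha. With an exact binomial, n = 60, null rate 20% and alternative 5%:

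- Reject the null at 6 or fewer events: alpha = P(X ≤ 6 | 0.20) = 0.031, power = P(X ≤ 6 | 0.05) = 0.970.
- Reject at 5 or fewer: alpha = 0.012, power = 0.921.

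Either way the stated power reproduces. It does not depend on the point made here.

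**The printed two-stage rule.** Let X1 and X2 be the events in the first and second 15 men, each Binomial(15, p). Accrual stops if X1 ≥ 3 or X1 + X2 ≥ 4, so

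P(stop) = 1 − Σ P(X1 = x) · P(X2 ≤ 3 − x), summed over x = 0, 1, 2.

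- p = 0.05: 1 − (0.4633 × 0.9945 + 0.3658 × 0.9638 + 0.1348 × 0.8290) = 1 − 0.925 = 7.5%.
- p = 0.15: 1 − (0.0874 × 0.8227 + 0.2312 × 0.6042 + 0.2856 × 0.3186) = 1 − 0.303 = 69.7%.
- p = 0.20, by the same formula: 88.6%.

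**How one event changes the decision.** Suppose the first 15 treated men are 14 eligible men with 2 events and 1 ineligible man with 1 event. Counting all treated men gives 3 of 15, a stop. Under the printed rule the ineligible man is dropped and a fifteenth eligible man is awaited. If he has no event, the count is 2 of 15 and accrual continues. An eligible-only count of exactly 2 in 15, one short of the boundary, has probability 13.5%, 26.7% and 23.1% at true rates of 5%, 10% and 20%.

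**Size if all treated men are counted.** Let s be the share of treated men who are ineligible, q their event rate and p the rate in eligible men. The documents give neither s nor q, and the 15% used for p is an assumed value between the plan's 5% and 20%. If each treated man is ineligible independently with probability s, the rate among all treated men is r = (1 − s)p + sq, which is put into the formula above in place of p. For example, p = 0.15, s = 0.10 and q = 0.50 give r = 0.135 + 0.050 = 0.185.

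| Eligible rate p | s | q | r | P(stop), all treated | P(stop), eligible only |
|---|---|---|---|---|---|
| 15% | 10% | 10% | 14.5% | 67.1% | 69.7% |
| 15% | any | 15% | 15% | 69.7% | 69.7% |
| 15% | 5% | 20% | 15.25% | 71.0% | 69.7% |
| 15% | 2% | 30% | 15.3% | 71.3% | 69.7% |
| 15% | 5% | 40% | 16.25% | 75.8% | 69.7% |
| 15% | 10% | 50% | 18.5% | 84.4% | 69.7% |
| 20% | 5% | 40% | 21% | 90.9% | 88.6% |
| 5% | 2% | 20% | 5.3% | 8.8% | 7.5% |
| 5% | 5% | 20% | 5.75% | 10.9% | 7.5% |
| 5% | 5% | 40% | 6.75% | 16.2% | 7.5% |
| 5% | 10% | 50% | 9.5% | 34.4% | 7.5% |

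The last four rows are the cost of the change: more closures when the regimen is acceptable in eligible men.

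**The case against.** The strongest reply is that the eligible-only rate is the right quantity for the population the trial is meant for. For that population it is not biased, and it reads low only if the target is all treated men and ineligible men also have higher risk. That is correct, and it is why the eligible-only count should stay visible as a sensitivity analysis.

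The direction is not certain either. Many entry criteria have no evident upward link with GU or GI toxicity: biopsy date, date of the rectal examination, PSA limits, age, metal implants, earlier malignancy. Symptom score, gland measurement and history are baseline items in Section 6.6, so the breaches of most concern should usually be found before treatment. The documents do not show how often one would surface later. This limits the expected size, but it does not settle how such an event is to be counted.

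A reader might infer that these events escape safety surveillance altogether. They do not: Section 6.8 records adverse events at each visit, and the reporting rules in Section 5.9 carry no eligibility limit. That is reporting case by case, however, and does not add to the 3 in 15 or 4 in 30. A reader might also infer a material delay to the look. At the planned 2 men a month, replacing one man takes about two weeks, which is trivial against a 24-month event window.

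**Conclusion.** The point holds in a limited form. Both statements of the definition exclude treated but ineligible men from the count, nothing elsewhere brings them back, and one such event can decide the outcome.

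The size is illustrative only. At a 15% eligible rate, counting all treated men changes the chance of stopping by 1 to 2 points under mild assumptions and by up to about 15 points under strong ones. It changes nothing at equal risk and lowers it by about 3 points if ineligible men have lower risk. At the 20% rate the rule is built to catch, the one case computed adds about 2 points.

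The documents do not support the stronger claims that the monitored rate is known to be biased downward or that ineligible men are known to have higher risk; the latter is plausible but not stated. Nor does the point touch the stated power. The general toxicity analysis under Section 7.1 has no eligible-only limit, so the defect lies in Section 7.4 alone.

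**What to change.** In the text of Section 7.4 and in the table footnote, define analyzable patients as all patients who received any protocol radiation, regardless of eligibility. Keep the looks at 15 and 30 and the printed boundaries. Let the review after a boundary is met cover the same men, and give the review team the eligible-only count alongside as a sensitivity analysis. Stating the analysis set for the toxicity endpoints under Section 7.1 would be a useful clarification, but corrects no error there.

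The drafting cost is one sentence in two places, with no change to sample size or data collection. The operating cost should be stated openly. If the eligible rate is truly 5%, the chance of a temporary closure rises from 7.5% to about 9% to 11% under mild assumptions (2% to 5% ineligible, 20% events), and to 16% to 34% with 5% to 10% ineligible and 40% to 50% events. Because meeting a boundary leads to review and a recommendation rather than automatic termination, the eligible-only count lets the team see when ineligible men account for the signal.
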